Race-based discrimination likely is an important contributor to health disparities. A meta-analysis of 192 studies demonstrates the association between perceived discrimination and mental health concerns (Pascoe & Smart Richman, 2009). Discrimination has been identified as a mediator of the relationship between minority status and mental health (Cokley, Hall-Clark & Hicks, 2011), even after controlling for personality traits (Mekawi et al., 2021) or combat exposure and military rank (Loo et al., 2001). Pervasive discrimination also predicts increased AL above and beyond other risk factors (Van Dyke et al., 2020). Perceived discrimination may impact health directly; a longitudinal study of Black Americans showed that increased frequency of racial discrimination predicted greater nonspecific psychological distress, depression symptoms, and days with poor mental health (Kwate & Goodman, 2015). Perceived discrimination also contributes indirectly to health status via medical mistrust, poorer health behavior, and decreased health care utilization (Bazargan, Cobb, & Assari, 2021; Lee, Ayers, & Kronenfeld, 2009; McClendon, Chang, et al., 2021). VOC show poorer control of clinical outcomes such as blood pressure, cholesterol and glucose (Trivedi, Grebla, Wright & Washington, 2011). **The rationale for the proposed intervention is to reverse the negative direct (e.g., chronic stress) and indirect (e.g., poorer health behavior) factors that sustain health disparities.**

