**Assessment approach.** Because of the history of human rights violations and misconduct in medical and psychological research, many people of color mistrust research activities (Suite, La Bril, Prim, & Harrison-[name], 2007). This is an important reason to study the feasibility of the proposed data collection strategy and motivation to prioritize brevity of our assessment battery. A record of study participation will be gathered following CONSORT guidelines to quantify enrollment and retention. Assessments will be completed within 1 month prior to the beginning of group and within 1 month after the end of group. The sample will be characterized at the baseline assessment. Participant characteristics including age, gender, race/ethnicity, education, work status and financial and housing stability, will be gathered using a demographic questionnaire. Adherence to group will be quantified based on attendance at sessions and proportion of homework completed (**coded as none/partial/complete as judged by the therapist**).

**Recruitment feasibility.** Aim 1 of this study involves evaluating strategies for recruiting VOC for this type of study. *Enrollment rate*, defined as the number of contacts per enrollment, will be used to optimize the future approach to accrual. There is no target enrollment rate as many can be acceptable; this metric will serve to guide resource allocation. **Gathering information from Veterans and providers about reasons for declining participation or referral, however, will be important in determining the representativeness of the sample.** *Number of enrollments per month* will be viewed as successful if at least four individuals are enrolled per month as that level of recruitment represents a reasonable period (average 2-3 weeks) for a Veteran to wait for a group to begin. *Initiation rate* will be defined as the proportion of Veterans who initiate the intervention among all consented participants. This will inform recruitment strategies (i.e., which strategies lead to the highest proportion of treatment initiation) but also may help to identify areas of improvement in terms of connecting Veterans to the project. As these behaviors are recorded prior to the first session, we do not expect group differences.

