**Allostatic load** will be assessed pre and post intervention by measuring 10 markers of interest, specifically hemoglobin (Hb) A1c, systolic and diastolic blood pressure (SBP, DBP), high density lipoprotein (HDL), triglycerides, urine epinephrine (Epi) and norepinephrine (NE), waking salivary cortisol, interleukin (IL)-6, and hsCRP. **Venous blood will be drawn via vena puncture between 8-10 AM after overnight fasting and sent to the VA clinical chemistry lab to measure Hb A1c and the lipid panel (for HDL and triglycerides). Plasma from 5mL of blood will be collected and frozen at -80 C until assayed to measure IL-6 and hsCRP using electrochemiluminescence assay (Mesoscale Discovery). Spot urine will be collected for Epi and NE and frozen at -80 C until assayed using ELISA-based immunoassay and adjusted for creatinine levels, which are well representative of general sympathetic output of an individual. Salivary cortisol levels will be measured in saliva collected the morning of the blood draw visit upon wakening. Saliva samples will be frozen at -80 C until assayed using immunoassay (Salimetrics). Both pre and post samples from a given participant will be assayed together using reagents from a single lot number by one technician who is blinded to the condition. All biomarker assays will be done in [name] lab where they are routinely performed, and the intra- and inter-assay CV's of these proposed markers are <10%. Seated SBP and DBP will be measured after a 5-min of rest, and the average from 3 readings will be used. The AL index for each participant will be calculated by assigning 1 to the highest quartile values vs. the rest 0 for each marker and summing them (Rosemberg, Granner, Li & Seng, 2020).** Thus, a possible range of 0 to 10 would emerge, indicating the lowest to highest AL across the participants. We acknowledge that there have been differing ways for AL index calculation as well as included markers. Our proposed methods and the markers are based on the best consensus from a number of studies and reviews that also demonstrated evidence of AL reflecting chronic stress and eventual health outcomes including all-cause mortality (Duong et al., 2017; Guidi, Lucente, Sonino, & Fava, 2021; Juster, McEwen & Lupien, 2010).

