**Sample size.** As a feasibility study, the decision about sample size is not about establishing sufficient power to detect change in clinical outcomes but rather about demonstrating the viability of a future larger-scale study. The sample size was determined based on practical and quantitative considerations. We will aim for enrollment of 4 groups of each type of intervention, each with approximately 6 Veterans (average 6, range 4-10), leading to a total sample size of approximately 48 (24/cell) in the 15-month recruitment period. This rate of enrollment would demonstrate feasibility of a larger future study in that we would demonstrate that a steady flow of adequately sized intervention groups can be recruited. Given that this is a pilot and feasibility study, we are looking for clinical signal and feasibility rather than examining efficacy. All sample size analyses were performed using statistical package R. A two-sided type I error of 0.05 was assumed.

The sample size assessment was conducted for assessing the enrollment and completion rates. First, we assessed the precision of estimates based on projected sample size. We considered a range of target rate from 0.60 to 0.90 and estimated the width of the 95% exact binomial confidence interval for enrollment and completion rates for overall and for each intervention group (see **Table 1**).

**Table 1.** The width of 95% confidence intervals for enrollment and completion rates

Sample size	Estimated rate						
	0.60	0.65	0.70	0.75	0.80	0.85	0.90
48	0.267	0.261	0.251	0.239	0.222	0.201	0.174
24	0.365	0.357	0.345	0.329	0.308	0.282	0.249

From **Table 1**, if an estimated intervention initiation rate is 0.80, a sample size of 48 (total) and 24 (per intervention group) will produce a two-sided 95% confidence interval with a width of 0.222 and 0.308,

respectively. If an estimated intervention initiation rate is 0.90, the width of the 95% CI is reduced (becomes more precise, see **Table 1**) with the same sample size projected above.

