As a feasibility study, the sample size was not projected to ensure enough study power for hypothesis testing. We assessed the effect size of the outcome (such as Brief PHI, DASS-21, TSDS) that can be detected with the planned sample size and 80% power. The effect size for change in outcome from baseline to post treatment in each intervention group and overall was estimated based on a paired t-test. With a sample size of 24 per group and 48 in total, we could detect an effect size of 0.60 and 0.41, which are moderate effect sizes. To compare the outcome change between the RBSTE and PCT groups, with 24 per group, we could detect a moderate effect size of 0.83 for the difference with 24 subjects per group. This effect size would be clinically meaningful thus signaling the need for additional study.

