We will assess four outcome measures for enrollment and retention: 1) *enrollment rate* defined as the proportion of consented subjects among all screened and eligible patients; 2) *initiation rate* defined as the proportion of subjects who initiate the intervention among all consented subjects; 3) *per protocol completion rate* defined as the proportion of subjects who complete 5 or 6 sessions of intervention among those who start the intervention; 4) *intent-to-treat completion rate* defined as the proportion of subjects who complete 5 or 6 sessions of intervention among all randomized subjects. The 95% CI (based on normal approximation or exact binomial test when appropriate) will be estimated for all these rates for overall and by each intervention group. The rates for the RBSTE and PCT groups will be compared by Fisher's exact test. Multivariable analysis will be also performed to examine the difference in outcomes between intervention groups using logistic regression.

**Aim 2:** *To understand Veterans' views of the acceptability and appropriateness of treatment content, the feasibility of participation, and perceptions of provider behavior and attitudes.*

The AIM, IAM, FIM and Provider Rating Scales will be estimated by mean, SD and 95% CI. Intervention groups will be compared by Wilcoxon rank sum test. Multivariable analysis will be also performed to examine the difference in outcomes between intervention groups using linear regression.

**Aim 3:** *To optimize the strategy for holistic evaluation of intervention effects.*

As aforementioned, we will include a comprehensive list of cardiometabolic, neuroendocrine, and inflammatory markers that had been shown as reliable markers of AL in the literature to derive an AL index for each participant. We hypothesize that AL index at baseline will be associated with perceived discrimination as well as other psychosocial outcomes and that pre to post-intervention changes of AL index will differ between the two groups. We will perform regression analysis and variable selection using LASSO (Tibshirani 1996) to identify a smaller subset of the AL markers at baseline that show significant associations with psychosocial outcome measures. The effect size for pre and post change in AL markers will be estimated. This will inform future efficacy and effectiveness studies in potential reduction of a list of biomarkers to enhance feasibility, efficiency and reduce participant burden.

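### The allostatic load index ignores drug treatment of four or five of its ten markers, which blurs its baseline associations and the LASSO marker selection; the effect on between-arm change is small

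*Combined protocol and SAP*

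**What the plan says.** The Allostatic load paragraph (Research Design and Methods) lists ten markers: HbA1c, systolic and diastolic blood pressure, HDL, triglycerides, urinary epinephrine and norepinephrine, waking salivary cortisol, IL-6 and hsCRP. The index "will be calculated by assigning 1 to the highest quartile values vs. the rest 0 for each marker and summing them". The paragraph standardizes fasting, draw time, reagent lot, technician blinding, creatinine adjustment and rest before blood pressure readings. It does not mention medication.

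The other places where medication might appear are also silent:

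- **Participants:** recruitment includes primary care, and no criterion concerns medication or its stability.
- **Assessment approach:** "Participant characteristics including age, gender, race/ethnicity, education, work status and financial and housing stability, will be gathered using a demographic questionnaire".
- **Analyses:** clinically important baseline variables may be screened as covariates, but none is named.

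Background and Significance states: "VOC show poorer control of clinical outcomes such as blood pressure, cholesterol and glucose". It also says that perceived discrimination affects health partly through medical mistrust and lower use of care.

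Under Aim 3 the plan states: "We hypothesize that AL index at baseline will be associated with perceived discrimination as well as other psychosocial outcomes". It further hypothesizes that AL change differs between arms, applies LASSO to the baseline markers to find a smaller set, and estimates pre-post effect sizes for the markers.

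**The concern.** A marker value on treatment reflects both underlying burden and the treatment. An index built only from measured values gives a treated Veteran a lower expected score than an untreated Veteran with the same burden.

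This matters most at baseline. On the plan's own premise, discrimination goes with less use of care, so treatment status may be related both to the exposure (discrimination) and to the measured markers. A positive association between AL and discrimination could then arise through chronic stress, through less treatment, or through both. Without medication data the investigators cannot say how much comes from each. The LASSO step could likewise keep or drop a marker partly because of who is treated, and a later trial would inherit that choice. Refining the assessment strategy is one of the three stated aims, so the question falls within what the pilot is meant to settle.

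For pre-post change, the exposure is to medication started, stopped or altered between visits. These are separated by 8 weeks of group plus up to 1 month on each side, about 8 to 17 weeks.

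**Working it through.** **1. The plan's own figures.** Inputs from Sample size: "A two-sided type I error of 0.05 was assumed"; 80% power; "leading to a total sample size of approximately 48 (24/cell) in the 15-month recruitment period". Noncentral-t calculations give detectable standardized effects of 0.597 (paired, n = 24), 0.413 (paired, n = 48) and 0.826 (two arms of 24). These match the stated 0.60, 0.41 and 0.83. The plan gives no figure for AL or for medication.

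**2. Marker count.** HbA1c, systolic and diastolic pressure and triglycerides make 4 of 10; with HDL, 5 of 10. The five-marker scenario below assumes that HDL is scored so that its adverse end earns the point. The scoring sentence does not say this.

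**3. Baseline distortion.** Assumptions, none from the documents: 40% of participants are treated; treatment lowers each affected marker by s = 0.5 or 1.0 SD; treated and untreated Veterans have the same underlying burden; markers are normal. The top-quartile cut c solves

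0.6 × [1 − Φ(c)] + 0.4 × [1 − Φ(c + s)] = 0.25.

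| s | c | P(point), untreated | P(point), treated | Gap per marker | 4 markers | 5 markers |
|---|---|---|---|---|---|---|
| 0.5 | 0.495 | 0.310 | 0.160 | 0.150 | 0.60 | 0.75 |
| 1.0 | 0.361 | 0.359 | 0.087 | 0.272 | 1.09 | 1.36 |

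Treated Veterans score about 0.6 to 1.4 points lower. A simulation with n = 48 and correlated markers gave the same range (0.6 and 1.1 for four markers, 0.76 and 1.36 for five).

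**4. What this does to an association.** In that simulation treatment was unrelated to stress, and the correlation between stress and the index fell only slightly, from about 0.73 to 0.67-0.72. The larger problem arises if treatment varies with discrimination. For illustration, if the treated share were 20 percentage points lower among Veterans reporting more discrimination, the index would differ by 0.20 × 0.60 = 0.12 to 0.20 × 1.36 = 0.27 points from treatment alone.

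**5. Between-arm change.** With cuts fixed at baseline and no true intervention effect, the expected shift is 0.6 (untreated share) × difference in start rates × the point gap from step 3.

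- Stable medication, or equal start rates: 0.
- Starts of 20% vs 5% among the untreated: 0.6 × 0.15 × 0.60 = 0.05 to 0.6 × 0.15 × 1.36 = 0.12 points. Simulated: 0.04 to 0.13 points, d 0.03-0.09.
- Starts of 40% vs 10%: 0.6 × 0.30 × 0.60 = 0.11 to 0.6 × 0.30 × 1.36 = 0.24 points. Simulated: 0.10 to 0.24 points, d 0.08-0.18, with the rejection rate at a nominal 5% rising to 6.5-9%.

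The largest of these, d = 0.18, compares with the stated detectable 0.83.

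**6. Chance imbalance.** With eight groups of six and 30-50% treated, the chance that the arms differ by 20 percentage points or more in baseline treatment is 16-19% without clustering, and 25-29% at an assumed intraclass correlation of 0.10.

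**The case against.** **The plan leaves some room for medication.** The characteristics list is introduced as non-exhaustive, the covariate screen could admit a medication variable, and the appendices were not available. This stands as a limit: the finding is that no text supplied provides for recording medication, not that it will certainly go unrecorded. The screen is only a partial answer, because it names no such variable, needs data to be collected, and covers baseline only.

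**Reduced care is part of the plan's theory.** The baseline hypothesis claims an association, not a stress-only route. This also stands. A reader might infer that any association found would be under-treatment rather than stress, but the documents treat both as routes from discrimination to health. The defect is that the two cannot be separated.

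**Randomization protects the change comparison.** Largely true. A reader might infer that medication changes would pass for an effect of RBSTE, picturing a Veteran who starts blood-pressure treatment and loses 2 points, about 1.5 index SDs. That needs the Veteran to be in the top quartile for both pressures and to leave both. The SD behind it, √(10 × 0.25 × 0.75) = 1.37, assumes independent markers, although the two pressures must move together for the example to work. At an assumed correlation of 0.25 between underlying markers the SD is 2.07, and 2 points is 2 / 2.07 = 0.97 SD. Nor is a medication change necessarily noise: RBSTE promotes proactive behavior and self-advocacy, so it may be a pathway of the intervention.

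**This is a pilot.** Its analyses are for feasibility and hypothesis generation, and no feasibility outcome depends on AL. That limits the weight of the point but does not remove it.

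**Conclusion.** The concern holds, chiefly for the baseline analyses. Scoring measured values alone, with no provision for medication data, puts treated Veterans about 0.6-1.4 points lower at equal burden. That range rests on assumed treatment rates and drug effects. It leaves the association of AL with discrimination, and the LASSO selection, open to more than one reading.

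It does not follow that every Veteran on treatment scores 0 on the treated markers. The cuts are sample quartiles, and a treated Veteran can still be above them.

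For pre-post change the effect is smaller. Balanced medication changes distort only the within-arm effect sizes. Between-arm bias needs unequal changes, and reaches d of about 0.18 only at assumed start rates of 40% vs 10%. The documents do not support reading this as a serious threat to the arm comparison.

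**What to change.** 1. At both AL visits, record current blood-pressure, lipid and glucose-lowering medication.
2. For the baseline associations and LASSO, report beside the planned index a sensitivity version that scores a marker 1 if it lies in the high-risk quartile or is under drug treatment. State the scored direction for each marker, HDL included. Note that this version can err the opposite way, because it adds points for Veterans with better access to care and none for undiagnosed disease. The two versions are best read together.
3. For pre-post change, keep the all-participants comparison as the main result and describe medication changes by arm. Label any analysis restricted to Veterans with stable medication as descriptive and non-randomized, since it selects on an event after randomization that the intervention may influence.

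The cost is a few minutes per visit and one extra analysis. Nobody's care changes.

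### Table 1 is labelled exact binomial but holds Wilson score widths, which are narrower than exact; its denominators of 48 and 24 do not fit the enrollment rate

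*Combined protocol and SAP*

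**What the plan says.** The Sample size paragraph of Research Design and Methods plans enrollment in groups, "leading to a total sample size of approximately 48 (24/cell) in the 15-month recruitment period". It disclaims power for clinical outcomes as the basis for that number and then assesses precision. "We considered a range of target rate from 0.60 to 0.90", it says, and the authors "estimated the width of the 95% exact binomial confidence interval for enrollment and completion rates for overall and for each intervention group". The error rate is given as "A two-sided type I error of 0.05 was assumed".

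Table 1 is titled "The width of 95% confidence intervals for enrollment and completion rates" and has rows for 48 and 24. The text below it takes a rate of 0.80, calls it an initiation rate, and says the two sample sizes "will produce a two-sided 95% confidence interval with a width of 0.222 and 0.308", respectively.

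Under Analyses, Aim 1, the enrollment rate is "defined as the proportion of consented subjects among all screened and eligible patients". It is listed with the initiation rate and two completion rates. For the four together, "The 95% CI (based on normal approximation or exact binomial test when appropriate) will be estimated for all these rates", overall and by intervention group, and the arms are to be compared by Fisher's exact test. The opening of Research Design and Methods places randomization after a cohort has enrolled and finished its baseline assessment.

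**The concern.** There are two separate problems.

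1. **Method.** Exact binomial intervals are conservative, and at these sample sizes they are wider than most alternatives. The tabulated widths looked too narrow for the method named. If so, the plan promises more precision for its feasibility rates than the exact interval will deliver. Estimating those rates is the purpose of the pilot, and Table 1 is the only calculation the plan offers on how precisely it can do so.

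2. **Denominator.** The planned 48 are people who have enrolled. They cannot also be the denominator of the proportion who enroll. Eligible people who decline are never assigned to an arm, so one of the four by-arm comparisons listed under Aim 1 could not be carried out.

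**Working it through.** **Inputs, all from the Sample size section:** n = 48 and 24; rates p = 0.60 to 0.90 in steps of 0.05; two-sided 95%, so z = 1.96 (z² = 3.8415).

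**Step 1. Reproduce Table 1.** The Wilson score width without continuity correction is

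2z·√[p(1−p)/n + z²/(4n²)] / (1 + z²/n).

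At p = 0.80:

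- n = 48: 2(1.96)·√(0.003333 + 0.000417) / 1.0800 = 0.2223. Table 1 gives 0.222.
- n = 24: 2(1.96)·√(0.006667 + 0.001667) / 1.1601 = 0.30848. Table 1 gives 0.308.

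The same formula returns all 14 cells to three decimals.

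**Step 2. Apply the named method.** With x = np, the Clopper-Pearson limits are the 2.5% quantile of Beta(x, n−x+1) and the 97.5% quantile of Beta(x+1, n−x).

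| Rate | n = 48, Table 1 | n = 48, exact | n = 24, Table 1 | n = 24, exact |
|---|---|---|---|---|
| 0.60 | 0.267 | 0.290 | 0.365 | 0.410 |
| 0.65 | 0.261 | 0.283 | 0.357 | 0.401 |
| 0.70 | 0.251 | 0.273 | 0.345 | 0.387 |
| 0.75 | 0.239 | 0.260 | 0.329 | 0.369 |
| 0.80 | 0.222 | 0.242 | 0.308 | 0.346 |
| 0.85 | 0.201 | 0.219 | 0.282 | 0.315 |
| 0.90 | 0.174 | 0.189 | 0.249 | 0.276 |

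No cell agrees. The exact width exceeds Table 1 by 8.5% to 9.0% at n = 48 and by 10.8% to 12.4% at n = 24, or 0.015 to 0.045 in absolute terms.

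**Step 3. Rule out rounding of counts.** Most np are not whole numbers, but at 0.75 both are. The exact width for 36/48 is 0.260 against 0.239 (8.6% wider), and for 18/24 it is 0.369 against 0.329 (12.3% wider). With np rounded to the nearest integer elsewhere, the excess runs from 4% (22/24) to 16% (20/24). At the highlighted rate, 38/48 gives 0.245 and 19/24 gives 0.350.

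**Step 4. Try the other methods.** The simple normal-approximation (Wald) width, 2z·√[p(1−p)/n], is 0.226 and 0.320 at 0.80 and matches no cell. Agresti-Coull, Jeffreys, mid-P, Blaker, continuity-corrected Wilson and 90% Clopper-Pearson do not reproduce the table either.

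**Step 5. Enrollment-rate denominator.** With 48 consented, the number screened and eligible is 48 divided by the rate.

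| Enrollment rate | Eligible (48/rate) | Exact width | Table 1, n = 48 |
|---|---|---|---|
| 0.60 | 80 | 0.224 | 0.267 |
| 0.70 | about 69 | 0.228 | 0.251 |
| 0.80 | 60 | 0.215 | 0.222 |
| 0.90 | about 53 | 0.175 | 0.174 |

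The overall enrollment rate would therefore be estimated about as precisely as Table 1 says, or better. The fault is the denominator, not a further loss of precision. No by-arm version can be formed, because eligible people who decline are never randomized.

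**The case against.** The strongest reply is that Aim 1 allows a normal approximation as well as an exact interval, and the Wilson interval inverts a normal-theory score test. On that reading the analysis could produce the tabulated widths. Even against Wald the differences are small: about 2% and 4% at a rate of 0.80, and at 0.90 Wald is narrower than the table (0.170 against 0.174, and 0.240 against 0.249). This stands as a limit on the claim: the overstatement is relative to the exact method. It does not rescue the table, because the Sample size section says exact and the plan nowhere names Wilson.

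Second, little depends on the error. The size was set mainly by practical considerations, the success criteria are thresholds on point estimates, and the Participants paragraph allows a sample of 24 to 60, over which the exact width at 0.80 runs from 0.346 to 0.215. That is fair, and it sets the weight of the point.

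Third, the opening of Analyses limits arm comparisons to those that are necessary and appropriate. That general proviso does not undo Aim 1, which explicitly asks for by-group intervals and a Fisher test for the listed rates.

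Fourth, the retained rates have denominator problems too. Per-protocol completion is taken over those who start, at most 48 and 24. By-arm initiation is taken over consented people, some of whom may leave before randomization. This is correct, and the fix should cover it.

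**Conclusion.** The concern holds. All 14 entries of Table 1 are Wilson score widths under an exact binomial label. Under the named method the intervals are 8.5% to 12.4% wider with counts taken as np, or 4% to 16% wider with counts rounded to integers. At the rate the text highlights, 0.222 and 0.308 should read 0.242 and 0.346. These figures treat participants as independent, as Table 1 does.

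The enrollment rate does not belong in a table based on 48 and 24: 48 is its numerator, and it has no per-arm value. The eligible counts in Step 5 assume that exactly 48 consent. The Recruitment feasibility paragraph adds a further inconsistency, since it defines the enrollment rate as contacts made for each enrollment, which is not a proportion.

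This is an error of labelling and stated precision. It should be corrected, but it gives no reason to change the sample size or design.

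**What to change.** - **Choose one interval method and use it throughout.** Either replace Table 1 and the two widths in the text with the exact values above, or name the Wilson score interval in both Sample size and Aim 1. The second option makes the Table 1 widths correct as printed and gives narrower intervals than exact.
- **Retitle Table 1** for initiation and completion rates. Note that 48 and 24 are upper limits for per-protocol completion.
- **Report the enrollment rate overall only**, over those screened and eligible. Remove it from the by-arm intervals, the Fisher test and the by-arm logistic regression. Reconcile its definition with the Recruitment feasibility paragraph.
- **State the denominator for by-arm initiation**, since a consented person who leaves before randomization has no arm.

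The cost is one corrected table or one change of method name, plus a few words of text. No extra participants or data are needed.
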